8.9.3 Subgroup analysis

All data summaries will be made by treatment cohort [previous TKI only/previous TKI and a platinum-based doublet chemotherapy (patients may have also received additional lines of treatment)].

8.9.4 Planned Analyses

No interim analyses are planned for this study.

The primary analysis of ORR will take place after all patients have completed at 3 months after the last subject enrolled, to allow opportunity for all patients to completed two RECIST follow-up assessments. At this time, DoR and safety/tolerability will also be summarised. The primary analysis CSR will report the analysis of ORR supported by duration of response, and safety and tolerability data.

The full CSR will report the analysis of all primary and secondary endpoints (including updated ORR and DoR, DCR, tumour shrinkage, PFS, OS, Safety HRQoL, QTc and PK) and summarise the exploratory endpoint of patient reported adverse events (PRO-CTCAE). This analysis will take place approximately 8 months after the last subject has been enrolled, to allow responding patients to have a DoR greater than 6 months.

All patients will continue to be followed up for an updated analysis that will occur between 12-24 months after the last patient has been enrolled. All endpoints will be updated and summarised in an addendum to the CSR.

An earlier summary of ORR (before all patients have completed two RECIST follow-up assessments) could be performed at the request of regulatory authorities or AZD9291 Steering Committee.

8.9.5 Sensitivity analysis

The same methods of analysis will be applied to analyse ORR, DoR, DCR and PFS based on the RECIST data assessed by the investigator.

8.9.6 Exploratory analysis

PRO-CTCAE

PRO-CTCAE data will be presented using summaries and descriptive statistics based on the Full Analysis Set and further details will be provided in the SAP.

Healthcare Resource Use

Healthcare Resource Use data will be presented using summaries and descriptive statistics, based on the Full Analysis Set and further details will be provided in the SAP.

Exploratory analysis of post progression endpoints

PFS2 and time to subsequent treatment will be analysed using the same methods as the analysis of PFS and further details will be provided in the SAP.

Summaries and analyses for other exploratory objectives will be documented in a separate analysis plan and will be reported outside the CSR in a separate report.

9. STUDY AND DATA MANAGEMENT BY ASTRAZENECA

9.1 Training of study site personnel

Before the first subject is entered into the study, an AstraZeneca representative will review and discuss the requirements of the Clinical Study Protocol and related documents with the investigational staff and also train them in any study specific procedures and the WBDC and ePRO system(s) utilised.

The Principal Investigator will ensure that appropriate training relevant to the study is given to all of these staff, and that any new information relevant to the performance of this study is forwarded to the staff involved.

The Principal Investigator will maintain a record of all individuals involved in the study (medical, nursing and other staff).

9.2 Monitoring of the study

During the study, an AstraZeneca representative will have regular contacts with the study site, including visits to:

- Provide information and support to the Investigator(s)
- Confirm that facilities remain acceptable
- Confirm that the investigational team is adhering to the protocol, that data are being accurately and timely recorded in the CRFs, that biological samples are handled in accordance with the Laboratory Manual and that study drug accountability checks are being performed
- Perform source data verification (a comparison of the data in the CRFs with the subject's medical records at the hospital or practice, and other records relevant to the study) including verification of informed consent of participating subjects. This will require direct access to all original records for each subject (e.g., clinic charts)
- Ensure withdrawal of informed consent to the use of the subject's biological samples is reported and biological samples are identified and disposed of/destroyed accordingly, and the action is documented, and reported to the subject.

The AstraZeneca representative will be available between visits if the Investigator(s) or other staff at the centre needs information and advice about the study conduct.

9.2.1 Source data

Refer to the Clinical Study Agreement for location of source data.

9.2.2 Study agreements

The Principal Investigator at each/the centre should comply with all the terms, conditions, and obligations of the Clinical Study Agreement, or equivalent, for this study. In the event of any inconsistency between this Clinical Study Protocol and the Clinical Study Agreement, the terms of Clinical Study Protocol shall prevail with respect to the conduct of the study and the treatment of subjects and in all other respects, not relating to study conduct or treatment of subjects, the terms of the Clinical Study Agreement shall prevail.

Agreements between AstraZeneca and the Principal Investigator should be in place before any study-related procedures can take place, or subjects are enrolled.

9.2.3 Archiving of study documents

The Investigator follows the principles outlined in the Clinical Study Agreement (CSA).

9.3 Study timetable and end of study

The end of the study is defined as 'the last visit of the last subject undergoing the study'.

The study is expected to start in Q2 2014 and to end by Q4 2016.

The study may be terminated at individual centres if the study procedures are not being performed according to GCP, or if recruitment is slow. AstraZeneca may also terminate the entire study prematurely if concerns for safety arise within this study or in any other study with AZD9291.

9.4 Data management by AstraZeneca

Data management will be performed by AstraZeneca Data Management Centre staff, according to the Data Management Plan. Adverse events and medical/surgical history will be classified according to the terminology of the latest version the Medical Dictionary for Regulatory Activities (MedDRA). Medications will be classified according to the AstraZeneca Drug Dictionary. Classification coding will be performed by the Medical Coding Team at the AstraZeneca Data Management Centre.

The data collected through third party sources will be obtained and reconciled against study data.

Data queries will be raised for inconsistent, impossible or missing data. All entries to the study database will be available in an audit trail.

The data will be validated as defined in the Data Management Plan. Quality control procedures will be applied to each stage of data handling to ensure that all data are reliable and have been processed correctly. The Data Management Plan will also clarify the roles and responsibilities of the various functions and personnel involved in the data management process.

When all data have been coded, validated, signed and locked, clean file will be declared. Any treatment revealing data may thereafter be added and the final database will be locked.

Serious Adverse Event (SAE) Reconciliation

SAE reconciliation reports are produced and reconciled with the Patient Safety database and/or the investigational site.

Data Management of genotype data

Any genotype data generated in this study will be stored in the AstraZeneca genotyping Laboratory Information Management System (LIMS) database, or other appropriate secure system within AstraZeneca and/or third party contracted to work with AstraZeneca to analyse samples.

Data associated with human biological samples

Data associated with biological samples will be transferred from laboratory(ies) internal or external to AstraZeneca.

10. ETHICAL AND REGULATORY REQUIREMENTS

10.1 Ethical conduct of the study

The study will be performed in accordance with ethical principles that have their origin in the Declaration of Helsinki and are consistent with ICH/Good Clinical Practice, applicable regulatory requirements and the AstraZeneca policy on Bioethics and Human Biological Samples.

10.2 Subject data protection

The Informed Consent Form will incorporate (or, in some cases, be accompanied by a separate document incorporating) wording that complies with relevant data protection and privacy legislation.

AstraZeneca will not provide individual genotype results to subjects, any insurance company, any employer, their family members, general physician or any other third party, unless required to do so by law.

Precautions are taken to preserve confidentiality and prevent genetic data being linked to the identity of the subject. In exceptional circumstances, however, certain individuals might see both the genetic data and the personal identifiers of a subject. For example, in the case of a medical emergency, an AstraZeneca Physician or an Investigator might know a subject's identity and also have access to his or her genetic data. Also Regulatory authorities may require access to the relevant files, though the subject's medical information and the genetic files would remain physically separate.

10.3 Ethics and regulatory review

An Ethics Committee should approve the final study protocol, including the final version of the Informed Consent Form and any other written information and/or materials to be provided to the subjects. The Investigator will ensure the distribution of these documents to the applicable Ethics Committee, and to the study site staff.

The opinion of the Ethics Committee should be given in writing. The Investigator should submit the written approval to AstraZeneca before enrolment of any subject into the study.

The Ethics Committee should approve all advertising used to recruit subjects for the study.

AstraZeneca should approve any modifications to the Informed Consent Form that are needed to meet local requirements.

If required by local regulations, the protocol should be re-approved by the Ethics Committee annually.

Before enrolment of any subject into the study, the final study protocol, including the final version of the Informed Consent Form, is approved by the national regulatory authority or a notification to the national regulatory authority is done, according to local regulations.

AstraZeneca will handle the distribution of any of these documents to the national regulatory authorities.

AstraZeneca will provide Regulatory Authorities, Ethics Committees and Principal Investigators with safety updates/reports according to local requirements.

Each Principal Investigator is responsible for providing the Ethics Committees/IRB with reports of any serious and unexpected adverse drug reactions from any other study conducted with the investigational product. AstraZeneca will provide this information to the Principal Investigator so that he/she can meet these reporting requirements.

10.4 Informed consent

The Principal Investigator(s) at each centre will:

- Ensure each subject is given full and adequate oral and written information about the nature, purpose, possible risk and benefit of the study
- Ensure each subject is notified that they are free to discontinue from the study at any time
- Ensure that each subject is given the opportunity to ask questions and allowed time to consider the information provided
- Ensure each subject provides signed and dated informed consent before conducting any procedure specifically for the study
- Ensure the original, signed Informed Consent Form(s) is/are stored in the Investigator's Study File
- Ensure a copy of the signed Informed Consent Form is given to the subject
- Ensure that any incentives for subjects who participate in the study as well as any provisions for subjects harmed as a consequence of study participation are described in the informed consent form that is approved by an Ethics Committee.

10.5 Changes to the protocol and informed consent form

Study procedures will not be changed without the mutual agreement of the International coordinating Investigators and AstraZeneca.

If there are any substantial changes to the study protocol, then these changes will be documented in a study protocol amendment and where required in a new version of the study protocol (Revised Clinical Study Protocol).

The amendment is to be approved by the relevant Ethics Committee and if applicable, also the national regulatory authority approval, before implementation. Local requirements are to be followed for revised protocols.

AstraZeneca will distribute any subsequent amendments and new versions of the protocol to each Principal Investigator(s). For distribution to Ethics Committee see Section 10.3.

If a protocol amendment requires a change to a centre's Informed Consent Form, AstraZeneca and the centre's Ethics Committee are to approve the revised Informed Consent Form before the revised form is used.

If local regulations require, any administrative change will be communicated to or approved by each Ethics Committee.

10.6 Audits and inspections

Authorised representatives of AstraZeneca, a regulatory authority, or an Ethics Committee may perform audits or inspections at the centre, including source data verification. The purpose of an audit or inspection is to systematically and independently examine all study-related activities and documents, to determine whether these activities were conducted, and data were recorded, analysed, and accurately reported according to the protocol, Good Clinical Practice (GCP), guidelines of the International Conference on Harmonisation (ICH), and any applicable regulatory requirements. The Investigator will contact AstraZeneca immediately if contacted by a regulatory agency about an inspection at the centre.

Appendix B
Additional Safety Information

FURTHER GUIDANCE ON THE DEFINITION OF A SERIOUS ADVERSE EVENT (SAE)

Life threatening

‘Life-threatening’ means that the patient was at immediate risk of death from the adverse event (AE) as it occurred or it is suspected that use or continued use of the product would result in the patient’s death. ‘Life-threatening’ does not mean that had an AE occurred in a more severe form it might have caused death (eg, hepatitis that resolved without hepatic failure).

Hospitalisation

Out-patient treatment in an emergency room is not in itself a serious AE, although the reasons for it may be (eg, bronchospasm, laryngeal oedema). Hospital admissions and/or surgical operations planned before or during a study are not considered AEs if the illness or disease existed before the patient was enrolled in the study, provided that it did not deteriorate in an unexpected way during the study.

Important medical event or medical intervention

Medical and scientific judgement should be exercised in deciding whether a case is serious in situations where important medical events may not be immediately life-threatening or result in death, hospitalisation, disability or incapacity but may jeopardise the patient or may require medical intervention to prevent one or more outcomes listed in the definition of serious. These should usually be considered as serious.

Simply stopping the suspect drug does not mean that it is an important medical event; medical judgement should be used.

Examples of such events are:

- Angioedema not severe enough to require intubation but requiring iv hydrocortisone treatment
- Hepatotoxicity caused by paracetamol (acetaminophen) overdose requiring treatment with N-acetylcysteine
- Intensive treatment in an emergency room or at home for allergic bronchospasm
- Blood dyscrasias (eg, neutropenia or anaemia requiring blood transfusion, etc) or convulsions that do not result in hospitalisation
- Development of drug dependency or drug abuse.

A GUIDE TO INTERPRETING THE CAUSALITY QUESTION

The following factors should be considered when deciding if there is a “reasonable possibility” that an AE may have been caused by the drug.

- Time Course. Exposure to suspect drug. Has the patient actually received the suspect drug? Did the AE occur in a reasonable temporal relationship to the administration of the suspect drug?
- Consistency with known drug profile. Was the AE consistent with the previous knowledge of the suspect drug (pharmacology and toxicology) or drugs of the same pharmacological class? Or could the AE be anticipated from its pharmacological properties?
- Dechallenge experience. Did the AE resolve or improve on stopping or reducing the dose of the suspect drug?
- No alternative cause. The AE cannot be reasonably explained by another aetiology such as the underlying disease, other drugs, other host or environmental factors.
- Rechallenge experience. Did the AE reoccur if the suspected drug was reintroduced after having been stopped? AstraZeneca would not normally recommend or support a rechallenge.
- Laboratory tests. A specific laboratory investigation (if performed) has confirmed the relationship?

A “reasonable possibility” could be considered to exist for an AE where one or more of these factors exist.

In contrast, there would not be a “reasonable possibility” of causality if none of the above criteria apply or where there is evidence of exposure and a reasonable time course but any dechallenge (if performed) is negative or ambiguous or there is another more likely cause of the AE.

In difficult cases, other factors could be considered such as:

- Is this a recognised feature of overdose of the drug?
- Is there a known mechanism?

Ambiguous cases should be considered as being a “reasonable possibility” of a causal relationship unless further evidence becomes available to refute this. Causal relationship in cases where the disease under study has deteriorated due to lack of effect should be classified as no reasonable possibility.

Clinical Study Protocol Appendix C

Drug Substance	AZD9291
Study Code	D5160C00002
Edition Number	1
Date	26 February 2014

**Appendix C
International Airline Transportation Association (IATA) 6.2 Guidance
Document**

LABELLING AND SHIPMENT OF BIOHAZARD SAMPLES

International Airline Transportation Association (IATA) classifies biohazardous agents into three categories

[[http://www.iata.org/whatwedo/cargo/dgr/Documents/DGR52_InfectiousSubstances\(DGR362\).pdf](http://www.iata.org/whatwedo/cargo/dgr/Documents/DGR52_InfectiousSubstances(DGR362).pdf)].

For transport purposes the classification of infectious substances according to risk groups was removed from the Dangerous Goods Regulations (DGR) in the 46th edition (2005). Infectious substances are now classified either as Category A, Category B or Exempt. There is no direct relationship between Risk Groups and categories A and B.

Category A Infectious Substances are infectious substances in a form that, when exposure to it occurs, is capable of causing permanent disability, life-threatening or fatal disease in otherwise healthy humans or animals. Category A pathogens are eg. Ebola, Lassa fever virus

- are to be packed and shipped in accordance with IATA Instruction 602

Category B Infectious Substances are infectious Substances that do not meet the criteria for inclusion in Category A. Category B pathogens are eg. Hepatitis A, B, C, D, and E viruses, Human immunodeficiency virus (HIV) types 1 and 2. They are assigned the following UN number and proper shipping name:

- UN 3373 – Biological Substance, Category B
- are to be packed in accordance with UN3373 and IATA 650

Exempt - all other materials with minimal risk of containing pathogens

- Clinical trial samples will fall into Category B or exempt under IATA regulations.
- Clinical trial samples will routinely be packed and transported at ambient temperature in IATA 650 compliant packaging
- http://www.iata.org/whatwedo/cargo/dgr/Documents/DGR52_PI650_EN.pdf
- **Biological samples transported in dry ice require additional dangerous goods specification for the dry-ice content.**
- IATA compliant courier and packaging materials should be used for packing and transportation and packing should be done by an IATA certified person, as applicable.

- Samples routinely transported by road or rail are subject to local regulations which require that they are also packed and transported in a safe and appropriate way to contain any risk of infection or contamination by using approved couriers and packaging / containment materials at all times. The IATA 650 biological sample containment standards are encouraged wherever possible when road or rail transport is used.

Clinical Study Protocol Appendix D

Drug Substance	AZD9291
Study Code	D5160C00002
Edition Number	1
Date	26 February 2014

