6.3.4 Causality collection

The Investigator will assess causal relationship between Investigational Product and each Adverse Event, and answer 'yes' or 'no' to the question 'Do you consider that there is a reasonable possibility that the event may have been caused by the investigational product?'

For SAEs causal relationship will also be assessed for other medication and study procedures. Note that for SAEs that could be associated with any study procedure the causal relationship is implied as 'yes'.

A guide to the interpretation of the causality question is found in [Appendix B](#) to the Clinical Study Protocol.

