6.7 Management of IP related toxicities

If a patient experiences a CTCAE grade 3 or higher and/or unacceptable toxicity (any grade) not attributable to the disease or disease-related processes under investigation, where the Investigator considers the AE of concern to be specifically associated with AZD9291, dosing will be interrupted and supportive therapy administered as required in accordance with local practice/guidelines.

If the toxicity resolves or reverts to \leq CTCAE grade 2 within 3 weeks of onset, treatment with AZD9291 may be restarted at the same dose (80 mg) or a lower dose (40 mg) using the rules below for dose modifications (Table 9) and with discussion and agreement with the AstraZeneca Study Team Physician as needed. There will be no individual modifications to dosing schedule in response to toxicity, only potential dose reduction or dose interruption.

If the toxicity does not resolve to \leq CTCAE grade 2 after 3 weeks, then the patient should be withdrawn from the study and observed until resolution of the toxicity.

Table 9 Dose interventions

Intervention	AZD9291 Dose
Starting Dose	80 mg

Table 9 **Dose interventions**

Intervention	AZD9291 Dose
Reduced Dose –1	40 mg

On resolution of toxicity within 3 weeks:

- If an AE subsequently requires dose interruption, AZD9291 may restart at the same dose or the reduced dose, on resolution/improvement of the AE at the discretion of the Investigator.

If new or worsening pulmonary symptoms (eg, dyspnoea) or radiological abnormality suggestive of interstitial lung disease is observed, an interruption in study treatment dosing is recommended, and the AstraZeneca study team should be informed. A questionnaire regarding the results of the full diagnostic workup (including high-resolution computed tomography (HRCT), blood and sputum culture, haematological parameters) will be sent to Investigators. It is strongly recommended to perform a full diagnostic workup, to exclude alternative causes such as lymphangitic carcinomatosis, infection, allergy, cardiogenic edema, or pulmonary hemorrhage. In the presence of confirmatory HRCT scans where other causes of respiratory symptoms have been excluded, a diagnosis of interstitial lung disease should be considered and study treatment permanently discontinued.

In the absence of a diagnosis of interstitial lung disease study treatment may be restarted following consultation with the AstraZeneca Study Team Physician.

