6.3.3 Variables

Previous text:

The following variables will be collect for each AE;

- AE (verbatim)
- The date when the AE started and stopped
- Maximum CTCAE grade/changes in CTCAE grade
- Whether the AE is serious or not
- Investigator causality rating against the Investigational Product (yes or no)
- Action taken with regard to investigational product
- Outcome.

Revised text:

The following variables will be collect for each AE;

- AE (verbatim)
- The date when the AE started and stopped

- **Changes in CTCAE grade (for skin reactions and diarrhoea only); maximum CTCAE grade for all other AEs**
- Whether the AE is serious or not
- Investigator causality rating against the Investigational Product (yes or no)
- Action taken with regard to investigational product
- Outcome.

Section of protocol affected:

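### Appendix B gives two opposite causality ratings for an adverse event whose dechallenge is ambiguous, and does not say which rule prevails

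*Supplement*

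**What the plan says.** Section 6.3.4 puts one question to the investigator for each adverse event, "Do you consider that there is a reasonable possibility that the event may have been caused by the investigational product", to be answered yes or no. It adds: "A guide to the interpretation of the causality question is found in" Appendix B. Section 6.3.3, as revised by Amendment 2, keeps this rating among the variables collected for every event.

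Appendix B first lists factors to weigh. They include time course, consistency with the known drug profile, dechallenge (resolution or improvement on stopping or reducing the drug) and absence of another cause. Three rules follow, in this order:

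- **Inclusion.** A reasonable possibility "could be considered to exist for an AE where one or more of these factors exist".
- **Exclusion**, in the sentence beginning *In contrast*. There is no reasonable possibility if none of the criteria apply, or "where there is evidence of exposure and a reasonable time course but any dechallenge (if performed) is negative or ambiguous", or if another cause is more likely.
- **Default.** "Ambiguous cases should be considered as being a" reasonable possibility, unless further evidence refutes this.

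Neither amendment changes Appendix B, so this is current text.

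**The concern.** The exclusion and the default both classify the whole case, and both name ambiguity. They send it in opposite directions. An investigator who stops at the exclusion answers no; one who reads on to the default answers yes. Each has followed the guide.

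The recorded rating is at stake. The study has a single arm and no Data Monitoring Committee (Section 6.8.1), so no control group is available to set against inconsistent attribution. Two further steps are worded in terms of relatedness. Section 6.3.2 asks the investigator to notify the sponsor of a serious event learned of at any time if a reasonable possibility is seen. Section 7.8 describes 28 days of follow-up for new treatment-related serious events in patients still on drug after the final data cut-off.

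**Working it through.** The plan states no figure here and no arithmetic applies. The check applies the three rules to one fixed case: exposure is documented, timing is reasonable, and no other cause is more likely. Only the dechallenge result varies.

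| Dechallenge | Inclusion | Exclusion | Default | Result |
|---|---|---|---|---|
| Positive | supports yes | not triggered | not needed | consistent |
| Ambiguous | supports yes | no | yes | direct contradiction |
| Negative | supports yes | no | does not clearly apply | tension with inclusion only |
| Not performed | supports yes | not triggered | not needed | consistent |

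**Ambiguous.** The exclusion's conditions are met in its own terms. The default's condition is met as well if an ambiguous dechallenge leaves the case ambiguous, which is its natural reading. The default yields only to refuting evidence, and an ambiguous result does not refute. Inclusion points to yes too, since time course is one of the listed factors. Nothing in the guide ranks the rules.

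**Negative.** A negative result is not an ambiguous one and is arguably the refuting evidence that the default allows for. The exclusion therefore meets only the inclusion rule, which is permissive in wording and which the words *In contrast* introduce an exception to. The guide does leave open how a negative dechallenge is weighed when a further factor, such as consistency with the known drug profile, is also met.

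**Not performed.** The qualifier in brackets in the exclusion keeps this case out of its dechallenge limb.

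Of the four outcomes, one produces the contradiction.

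The places where the rating is used were then checked:

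- Section 6.4 requires all serious events to be reported whatever their causality, so it is unaffected.
- Sections 8.5 and 8.9.2 describe adverse events by preferred term and CTCAE grade, so they are unaffected.
- Sections 6.3.3 and 6.3.4 record the rating itself, so they are affected.
- Sections 6.3.2 and 7.8 are worded in terms of relatedness, so they can be affected.

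**The case against.** The strongest defence is that the default is a tie-breaker for the case as a whole, while the exclusion deals with one factor. That reading is possible, but the text does not state it, and the exclusion also ends in a verdict on the whole case.

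It can also be said that little hangs on the rating. Much of this stands. Serious events are reported regardless of causality. Deaths not clearly due to progression, or of unknown cause, are reported as serious events (Section 6.3.10). Appendix E assigns a related rating to agreed Hy's Law cases. An event that begins after the last dose has no dechallenge in the ordinary sense, which narrows the effect on Sections 6.3.2 and 7.8. Section 6.3.1 also words the collection of serious events after database lock without a relatedness condition.

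A reader might infer more than the documents support:

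- *That fatal or irreversible toxicities will tend to be rated unrelated.* A death on drug without dechallenge lies outside the exclusion because of its bracketed qualifier. A toxicity that persists after the drug is stopped is a negative dechallenge, which is a different case from the one in contradiction. No data in the documents show how often either occurs.
- *That the toxicity rules of Section 6.7 would fail to start.* Interruption there applies "where the Investigator considers the AE of concern to be specifically associated with AZD9291". Attribution comes first, before any dechallenge has taken place.
- *That related-event counts in the report are distorted.* The documents shown specify no such count. Details are left to an analysis plan that is not among them.

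**Conclusion.** The contradiction is real but confined to an ambiguous dechallenge with fitting exposure and timing and no more likely cause. In that case the guide supports both yes and no, so the recorded rating can differ between sites for the same event. Notification under Section 6.3.2 and follow-up under Section 7.8 can in principle differ with it.

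No rate can be attached: the documents do not give the frequency of ambiguous dechallenges, and any number would be invented. The primary endpoint, routine reporting of serious events and the adverse event summaries described are untouched. The conclusion assumes only that investigators apply the guide as written and that an ambiguous dechallenge can leave a case ambiguous. The change is worth making because it is small and makes a safety variable consistent.

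**What to change.** In the *In contrast* sentence of Appendix B, delete *or ambiguous* after *negative*. Add: *An ambiguous dechallenge is handled under the rule for ambiguous cases and does not by itself rule out a reasonable possibility.*

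The sponsor should also state how a negative dechallenge is weighed when another listed factor is met, for example consistency with the known drug profile. Removing a negative dechallenge altogether as evidence against causality would be a change of policy, and resolving the contradiction does not require it.

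The cost is one phrase removed, a sentence or two added and a note to sites. The downside is that slightly more adverse events will be rated related, which is the cautious direction that the guide's own default already takes.
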